- Obtain photographs (if treatment is given, ensure photos are taken prior to injection)

Effective

Version: 10.0

	Title 43USTT1904 CSP Infraorbital Hollows	Doc id MA-40833
--	---	---------------------------

- Assessments to be performed, prior to optional treatment:
 - GIHS - Treating Investigator and Blinded Evaluator
 - GAIS – Treating Investigator and Subject

CCI

For subjects receiving optional treatment

- Assess whether optimal aesthetic result has been achieved by subjects randomized to treatment (as agreed by the Treating Investigator and subject) and determine whether optional treatment or if initial treatment is appropriate.
 - Subject must meet eligibility criteria for treatment to be provided.
 - Treatment should not be provided if the subject has a disease or condition described in the exclusion criteria, or an ongoing treatment-related AE that in the opinion of the Treating Investigator would be worsened by a treatment.

If treatment is to be performed:

- Prior to any treatment being provided, perform UPT for all females of childbearing potential. The test result must be negative for a subject to receive the touch-up treatment.
 - Perform Vision Function Assessments prior to injection.
 - Subjects will be injected with the study product.
 - Record all concomitant medications/procedures used during the injection session.
 - Record the number of syringes used and the volume of study product injected during the injection session.
 - Evaluate for device deficiencies. If deficiencies are noted, complete form as specified in Section 8.6.
 - Following 30 minutes after injection, perform Vision Function Assessments.
 - Dispense new Subject Diary and remind subject on Diary completion. Remind the subject to bring the diary to next on-site study visit.
 - Schedule the 72 hours (\pm 24 hours) follow-up phone call (Visit 8a), Visit 8b, 14 days (\pm 3 days) and Visit 8c, 1 months (+ 7 days) after optional treatment (Visit 8).

For subjects who do not receive an optional treatment:

- Complete end of study form in the eCRF.

4.7.11 Visit 8a: Follow-up 72 hour (\pm 24 hours) telephone call after optional treatment

This visit should only be conducted for subjects who received a treatment at Visit 8.

- Interview subject regarding any concomitant therapies.

	Title 43USTT1904 CSP Infraorbital Hollows	Doc id MA-40833
--	---	---------------------------

Effective date: 2021-12-15 20:29

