10.7 Handling of drop-outs and missing data

Number of missing values will be summarized and reported as appropriate.

For mITT analysis of the Blinded Evaluator GIHS responder rate at month 3 after baseline (primary endpoint), CCI. Impact of missing data on the primary endpoint will be evaluated by performing sensitivity analysis based on the baseline observation carried forward (BOCF) method, and the observed cases.

	Title 43USTT1904 CSP Infraorbital Hollows	Doc id MA-40833
--	---	---------------------------

All other effectiveness endpoints will be evaluated based on the observed cases in ITT.

Descriptive statistics of all safety data will be performed on observed cases in the Safety population.

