### 1.1 Background

#### 1.1.1 Study design

This is a prospective, randomized, evaluator-blinded, no-treatment controlled, parallel group, multicenter US study to evaluate the effectiveness and safety of Restylane-L for correction of Infraorbital Hollows (IOH). Eligible subjects randomized to receive treatment will be injected by the Treating Investigator at Day 1. Optional touch-up treatment may be administered after 1 month of initial treatment, if deemed necessary by Treating Investigator and subject to obtain optimal aesthetic improvement. Optimal aesthetic improvement is defined as at least 1 grade improvement, from baseline, on the GIHS and best correction that can be achieved as agreed by the Treating Investigator and the subject.

At the month 12 visit, the no-treatment comparator subjects will be offered an optional Restylane-L treatment. The subjects who received Restylane-L at the baseline visit will also be offered an optional additional treatment if optimal aesthetic improvement is not maintained (as determined by the Treating Investigator and subject). For subjects receiving optional treatment at month 12 the effectiveness and safety data will be collected for another 6 months. A subject will be involved in the study for up to 19 months including 30 days screening and 6 months follow-up after optional treatment at month 12. The study flow chart is provided in Appendix A.

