#### 2.2 Analysis Populations

There will be three analysis populations defined for this study:

- Modified Intention-to-treat (mITT) Population Includes all subjects who are randomized
  and will be analyzed according to the randomization scheme; subjects with a GIHS Month 3
  assessment via a remote visit (i.e. remote office visit and/or GIHS assessment done
  remotely) will be excluded
- Intention-to-treat (ITT) Population Includes all subjects who are randomized at baseline and will be analyzed according to the randomization scheme determined at baseline
- Per protocol (PP) Population Includes all subjects in mITT who complete 3 months after baseline visit without any deviations considered to have substantial impact on the primary effectiveness
- Safety Population Includes all subjects who are treated with Restylane-L or randomized to the control group, and will be analyzed according to as-treated principle

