#### 2.5.2 Adverse events

All AE data will be summarized by needle, cannula, and no treatment separately. Only AEs occurring after first injection, for subjects randomized to Restylane-L or after randomization for subjects randomized to No Treatment, or AEs that worsened, will be included in analysis. AEs occurring before, if any, will only be listed in subject data listings.

	Title 43USTT1904 Statistical analysis plan - Tear Trough	Doc id
GALDERMA		MA-42205

2022-08-17 17:26

All AE endpoints will be presented by the timepoint in which they occurred, defined as:

- No Treatment at Baseline: For subjects randomized to No Treatment, an AE which starts between date of randomization up until the time of their first injection.
- Initial Treatment with Restylane-L: For subjects randomized to Restylane-L, an AE which starts on or after their baseline injection up until their optional retreatment (including optional touch-up); for subjects randomized to No Treatment, an AE which starts on or after their optional initial treatment.
- Retreatment with Restylane-L: For subjects randomized to Restylane-L, an AE which starts on or after their optional retreatment.

Missing dates, severity, relationship, and seriousness will be imputed as described in Section 2.4.2. Adverse Events will be summarized by SOC and PT. The MedDRA version used for the coding will be noted as a footnote in the tables and listings.

A summary of AEs will be provided, which will include the number and percentage of subjects and number of events with the following categories of:

- Any AE
- Any Serious AE
- Any AE related to study product or injection procedure
- Any Serious AE related to study product or injection procedure
- Any AE unrelated to study product or injection procedure
- · Any Serious AE unrelated to study product or injection procedure
- Any AESI
- Any Serious AESI
- Number of subjects who did not have an AE

Summaries of related AEs (including the total number of events, number and percentage of subjects) will be displayed by treatment grouping specified above according to the following:

- All AEs related to study product or injection procedure by SOC, PT, and maximum intensity (mild, moderate, or severe)
- All AEs related to study product or injection procedure by SOC, PT, and duration of event
- All AEs related to study product or injection procedure by SOC, PT, and number of days to onset of event

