- All AEs by SOC, PT, and action taken (none, medical treatment, non-pharmacological treatment, subject withdrawn)
- All AEs unrelated to study product or injection procedure by SOC, PT, and maximum intensity (mild, moderate, or severe)

For the subject level analyses, the number and percentage of subjects who experienced at least one of the events listed above will be summarized overall and for each SOC and each PT. System organ class and PTs will be presented in descending frequency first (by treatment group), and then alphabetically if there are ties. Each subject will contribute at most one count per summarization category. In other words, if a subject has more than one AE with same PT, the subject will be counted only once for that PT. Similarly, if a subject has more than one AE for a SOC, the subject will be counted only once in that SOC and PT. For the event level analyses, the counts of each respective event will be presented. In general, percentages) will be calculated using the number of subjects in the Safety population for the denominator.

[figure not shown]
2022-08-17 17:26

For the "action taken" summary specifically, subjects will be only counted in 'None' category if no other action was taken. For the onset/duration summaries, number of days to onset and duration of event will be summarized by SOC and PT, using mean, SD, minimum, maximum, and median statistics. Time to onset of an AE will be derived as the start date minus the date of most recent treatment. Duration of an AE will be derived as the stop date minus the start date + 1. Imputation rules for partial/completely missing dates are specified below. Missing stop date will not be imputed and therefore no duration will be calculated in these cases. Instead, the number of AEs that were ongoing at the end of the study will be given.

All reported AEs will be listed in data listings including time to onset, duration of AE, action taken (if applicable) and severity. By-subject listings also will be provided for all subjects for the following: Pre-treatment and AEs, AE severity, AEs related to study product or injection procedure, serious adverse events (SAEs), AEs leading to discontinuation of study drug, action taken, and resolution or outcome.

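### SAP 2.5.2 gives AE percentages by treatment period but states no denominator limited to subjects who entered the period, so the stated default understates Retreatment percentages

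*SAP*

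**What the plan says.** SAP 2.5.2 sets the layout: "All AE endpoints will be presented by the timepoint in which they occurred". Of the three periods, Retreatment is defined as "For subjects randomized to Restylane-L, an AE which starts on or after their optional retreatment". The overall AE summary gives numbers and percentages of subjects and numbers of events. It includes rows for AEs of special interest and a row for subjects without any AE. The more detailed summaries "will be displayed by treatment grouping specified above according to the following".

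For the denominator, the same section says: "In general, percentages) will be calculated using the number of subjects in the Safety population for the denominator". SAP 2.2 defines the Safety population: "Includes all subjects who are treated with Restylane-L or randomized to the" control group, analysed as treated. Membership does not depend on retreatment. Protocol 10.7 adds: "Descriptive statistics of all safety data will be performed on observed cases in the Safety population".

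Not everyone reaches the Retreatment period. Under SAP 1.1.1, subjects given Restylane-L at baseline are "offered an optional additional treatment if optimal aesthetic improvement is not maintained" at Month 12. Protocol 4.7.10 (Visit 8) then has a branch headed "For subjects who do not receive an optional treatment", under which the end-of-study form is completed at that visit. Footnote 4 to the schedule of events (Protocol Table 1) makes Visits 8a to 8e conditional on treatment being given.

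**The concern.** A subject who is not retreated cannot have a Retreatment-period AE, yet remains in the Safety population. Under the stated default that subject adds one to the denominator and nothing to the numerator. The printed percentage then mixes two things: how often events follow a repeat injection, and how many subjects had one. At identical incidence, Retreatment would look safer than Initial Treatment simply because fewer subjects entered it. The AE of special interest rows, which cover visual disturbances, would be affected in the same way. The row for subjects without an AE would move in the opposite direction, because it would take in people who were never exposed.

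A second programmer could reasonably use the number retreated instead and obtain different percentages from the same SAP.

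**Working it through.** **Inputs from the documents.** SAP 2.7 plans 146 needle, 136 cannula and 47 control subjects. These agree with its totals: 146 + 136 = 282 and 282 + 47 = 329. They are planned randomized numbers, used here in place of the Safety Ns on the assumption that everyone randomized to Restylane-L is injected.

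**Inputs not in the documents.** The fraction retreated and the AE incidence after retreatment are not given. For illustration only, uptake is taken as 30%, 50% or 70% and incidence as 20%. The plan prints no AE percentage to reproduce.

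**Formula.** Let x be the number of retreated subjects with an AE, r the number retreated and N the Safety subjects in the displayed column.

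- Incidence among retreated subjects = x/r.
- Printed percentage = x/N = (x/r) × (r/N).
- Relative shortfall = 1 − r/N, whatever the incidence.

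**Pooled Restylane-L column, N = 282.**

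| Assumed uptake | r | r/N | Shortfall | True 20% prints as | Row without an AE (should be 80%) |
|---|---|---|---|---|---|
| 30% | 85 | 0.301 | 69.9% | 6.03% | 94.0% |
| 50% | 141 | 0.500 | 50.0% | 10.00% | 90.0% |
| 70% | 197 | 0.699 | 30.1% | 13.97% | 86.0% |

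**Separate columns.** Needle (N = 146; r = 44, 73, 102) and cannula (N = 136; r = 41, 68, 95) both give 6.03%, 10.00% and 13.97%.

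**Rule of thumb.** Each 10% of subjects not retreated (0.10 × 282 = 28.2) lowers a Retreatment percentage by 10% of its value. The shortfall is zero only if every subject in the column is retreated.

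**Initial Treatment.** This period also takes in controls first injected at Month 12; controls never injected stay in the Safety population but do not enter it. In a column pooling all 329, the factor lies between 282/329 = 0.857 (no control injected) and 1 (all injected). If about half accept (assumed, 24 of 47), it is 306/329 = 0.930.

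**The case against.** The best defence is that period-specific Ns are already implied. Protocol 10.7 limits safety descriptives to observed cases, SAP 2.2 invokes the as-treated principle, and SAP 2.5.2 displays results by the treatment groupings it has just defined. Subjects who left at Month 12 could reasonably be called unobserved in Retreatment. That reading is possible, but none of these phrases says who is at risk in a period. Nor does the SAP 2.1 rule leaving missing counts out of percentages settle it: someone who never entered a period has no AE record, which is different from a missing value.

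Other parts of the defence stand. The denominator sentence is only a general default. It contains an unmatched parenthesis, which may be a typing slip or a sign of lost text. Parts of SAP 2.4 and 2.4.2 are blacked out, and the table shells are not in the file. An exception may exist there.

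Three stronger readings are tempting but not supported:

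- A reader might infer that all 329 subjects are the denominator everywhere. SAP 2.5.2 summarizes AEs separately for needle, cannula and no treatment, so column Ns are the natural reading. With 329 throughout, even No Treatment at Baseline, which only the 47 controls can enter, would be scaled by 47/329 = 0.143.
- A reader might infer that silence is deliberate, because SAP 2.3.2.1 (out-of-window visits) and 2.5.4 (Snellen acuity) spell out their denominators. But the GAIS response rates (2.4.4.2), the diary symptoms (2.5.3) and the other two vision tests (2.5.4) have no stated visit or period denominator either.
- A reader might infer that the sponsor chose a diluted denominator, or that the tables will be wrong. The text shows only a default that gives this result if it is followed as written.

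**Conclusion.** The point holds as a minor correction to descriptive tables. A percentage by period needs a denominator by period, and the readable AE text supplies only a general one that ignores entry into the period. Following it scales every Retreatment percentage by r/N. That factor is exact arithmetic, but its value is unknown because the documents do not give uptake. The 6%, 10% and 14% figures rest on the assumed uptakes and the assumed 20% incidence, and are not forecasts. The Initial Treatment effect is smaller: in a column pooling all 329 the shortfall is at most 14.3% (1 − 0.857).

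The consequences are limited. Protocol 10.5 makes safety analysis descriptive, so no test depends on this. Event counts and listings are unaffected. SAP 2.5.1 reports the number of subjects treated for each treatment separately, so a reader could recompute the rates. Confidence is moderate because unseen text could already supply the period Ns.

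**What to change.** Add to SAP 2.5.2 that the denominator for each period, within each displayed column, is the number of Safety subjects who entered that period:

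- No Treatment at Baseline: subjects randomized to control.
- Initial Treatment: all subjects given a first Restylane-L injection, including former controls injected at Month 12.
- Retreatment: subjects randomized to Restylane-L who were retreated.

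Print that N in the column headers and apply the same restriction to the row for subjects without an AE. If the observed-cases wording in Protocol 10.7 was meant to give these Ns, say so in the same place.

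The cost is one sentence and the column-N definitions in the AE tables. No new data are needed, since the counts treated are already planned. Unless everyone is retreated, any non-zero Retreatment AE percentage will be higher than under the stated default.

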#### Handling of Missing/Partial Dates

While every effort will be made to obtain complete information on every reported AE, the following imputation rules will be followed for any respective missing AE data:

GALDERMA

Title
43USTT1904 Statistical analysis plan - Tear Trough

MA-42205

Print date:

2022-08-17 17:26

#### 2.5.3 Pre-defined, Expected, Post-Treatment Events

Number and percentage of subjects reporting each pre-defined, expected, post-treatment symptom (i.e. Pain, Tenderness, Redness, Bruising, Swelling, Itching, Lumps/Bumps for each side of face), as collected in the 28-day diary, will be presented in total and by maximum severity (Tolerable, Affects daily activities, Disabling). Number of days with the event will be summarized by treatment period using the following categories: 1, 2-7, 8-13, and 14-28 days. If a subject completes more than one diary for a given treatment period, only the first diary (i.e. the diary with earlier entry dates) will be summarized in the table.

All subject diary data will be presented by treatment and subject in a data listing.

[figure not shown]

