3.1.3 Safety objectives and endpoints

The safety objectives and endpoints are:

- To evaluate AEs at all visits, and pre-defined, expected post-treatment events reported during the first 28 days after treatment as recorded in the subject diary.

4. Design of the Study

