#### 1.5.3 Subject Study Diary

Subjects will complete a 28-day symptom diary, starting on the day of injection, for each treatment (initial, optional touch-up, optional re-treatment).

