#### Injection Volume Administered

The injection volume (mL) administered throughout the study will be presented descriptively by the following timepoints, by group (where applicable):

- Initial treatment The amount of study product injected into subjects at the baseline visit (for subjects randomized to Restylane-L) or at the Month 12 visit (for subjects randomized to No Treatment).
- Optional Touch-up The amount of study product injected into subjects at the Month 1 visit. Only applicable to subjects randomized to Restylane-L.
- Initial treatment + Touch-up The cumulative sum of study product injected into subjects for the initial and touch-up treatments, regardless of how many treatments a subject received. This will be presented for both treatment groups.
- Re-Treatment The amount of study product injected into subjects at the Month 12 visit.
   Only applicable to subjects randomized to Restylane-L.
- Total injected volume The cumulative sum of study product injected into subjects across
  every potential injection timepoint, regardless of how many injections a subject got. This
  will be presented for both treatment groups.

If a subject receives more than one injection for a given treatment period, their total volume from all injections will be summarized in the 'Total injected volume' timepoint. Only the injection given closest to the protocol-specified injection visit (Appendix G) will be presented in each respective timepoint section described above.

All injection volume, injection characteristics, procedural anesthetics, and injection concomitant procedures data will be presented by treatment and subject in data listings.

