#### 2.9 Change History

The table below outlines the changes made to the SAP since the previous version.

Table 3. Changes from Previous Version

Version	Date	Description of Changes
2.0	06 OCT 2020	
 
Increased the number of subjects to be randomized
 
Added the mITT analysis population
 
Included the new COVID-19 protocol deviation categories
 
Updated the planned protocol deviation analysis
 
Updated the primary analysis method to be conducted using the mITT population
 
CCI
 
Updated the missing data sensitivity analyses to include: CCI
 
BOCF, ITT observed cases, tipping analysis using the mITT population, tipping point analysis using the ITT population
 
Added type of Month 3 visit (onsite, remote) as another subgroup analysis of the primary endpoint
 
Updated the sample size calculation
 

3.0	16 DEC 2021	Updated the MI methods for CMH test (Appendix H)     Updated primary analysis and secondary GIHS analysis method to be the CMH test  CCI

GALDERMA  Title  43USTT1904 Statistical analysis plan - Tear Trough	Doc id MA-42205
---	--------------------

2022-08-17 17:26

 
Updated Snellen Visual Acuity analysis
 
Added Section 2.3.2.1 to describe out of window visit duration analysis
 
Added information to Table 2
 
Added handling of data for injection characteristics, extent of exposure, and diary analyses for subjects injected multiple times in a treatment period.
 

 
Included information on statistical methods updates in section 2.4
 
Updated secondary analysis to present Months 3 and 6 after optional treatment as descriptive only
 
Updated tipping point analysis method to CMH
 

Doc id 43USTT1904 Statistical analysis plan - Tear Trough GALDERMA MA-42205

Print date:

2022-08-17 17:26

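### The diary table uses only the first diary in a treatment period, so symptoms recorded after a further injection in that period are left out

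*SAP*

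**What the plan says.** SAP 1.5.3 sets the data collection: "Subjects will complete a 28-day symptom diary, starting on the day of injection, for each treatment", and it names initial, optional touch-up and optional re-treatment as the treatments. SAP 2.5.3 then counts subjects with each of seven symptoms, in total and by maximum severity, and adds: "Number of days with the event will be summarized by treatment period using the following categories: 1, 2-7, 8-13, and 14-28 days". Where a subject has several diaries in one such period, "only the first diary (i.e. the diary with earlier entry dates) will be summarized in the table". The remaining diaries are kept elsewhere: "All subject diary data will be presented by treatment and subject in a data listing".

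The change history (SAP 2.9, version 3.0) records this rule together with those for injection characteristics and exposure, as handling of "diary analyses for subjects injected multiple times in a treatment period". The volume rule in SAP 2.5.1 is of the same kind. "Only the injection given closest to the protocol-specified injection visit" enters each timepoint row, while the total row sums every injection.

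Protocol 3.1.3 makes diary events a safety endpoint, "reported during the first 28 days after treatment as recorded in the subject diary". The protocol synopsis and section 8.3 make clear that this means each treatment. Protocol 10.5 describes the same table with the same day categories and no restriction to the first diary.

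**The concern.** A completed safety record is set aside by rule. For a subject with two diaries in a period, the maximum severity in the table is the maximum of the first diary only. A symptom that appears for the first time in the second diary is not counted.

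Diary tolerability is a named safety endpoint, and protocol 8.3 has it analysed and displayed apart from adverse events, so the AE tables do not make up for the loss. A by-subject listing gives no rates. The visible text offers no reason for preferring the first diary.

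The extent of the loss depends on what a treatment period is, and SAP 2.5.3 does not say.

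**Working it through.** The documents state no figure for this point, so there is none to reproduce. The check covers direction, meaning, timing, size and the volume rows.

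**1. Direction.** Take a subject with diaries 1 and 2 in one period and an unchanged denominator.
- Incidence: the symptom is present in diary 1 or 2 at least as often as in diary 1 alone.
- Severity: max(s1, s2) ≥ s1.
- Days: the days with symptoms over both diaries are at least those in diary 1.

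Using diary 1 alone can therefore only leave each summary equal or lower.

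**2. What a treatment period is.** The relevant sections, side by side:
- SAP 1.5.3 assigns a diary to each of initial, touch-up and re-treatment.
- SAP 2.5.1 (Injection Characteristics) lists the same three treatments, summarises each separately, and then uses the term treatment period for its keep-one rule.
- SAP 2.5.1 (Injection Volume Administered) gives touch-up its own row and adds a combined row for initial plus touch-up. If touch-up lay inside the initial period, the keep-one rule would treat every touch-up as a surplus injection and the touch-up row would have no purpose.
- SAP 2.9 shows the exposure and diary rules were added as one item with one term.
- SAP 2.5.2 differs: its initial-treatment timepoint takes in an event that "starts on or after their baseline injection up until their optional retreatment (including optional touch-up". But it defines timepoints for AEs and does not use the term treatment period.

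Four places point to touch-up as a separate period. One, in different terms, points the other way.

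**3. Can the first diary stand in for the later one?** The initial diary covers study days 1 to 28. Touch-up is due at 4 weeks (+7 days), which is study day 1 + 28 = 29 to 1 + 35 = 36. The two do not overlap. For an extra injection on study day d ≤ 28, the initial diary covers days d to 28, that is 29 − d days, provided it is kept to the end. From day 29 on it covers none.

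**4. Size, with touch-up as a separate period.**
- Subjects treated at baseline: 146 + 136 = 282 (protocol 4.1).
- Share x with an extra injection and second diary in the initial period: not given; assumed 2% to 5%.
- Diaries omitted: 282 × 0.02 = 5.6, about 6; 282 × 0.05 = 14.1, about 14.
- Incidence over all diaries: p1 + x(1 − p1)p2, where p1 and p2 are the symptom risks after the first and the extra injection, assumed equal and independent.
- p1 = p2 = 30%: 0.02 × 0.7 × 0.3 = 0.0042 and 0.05 × 0.7 × 0.3 = 0.0105, so 30% becomes 30.4% to 31.05%. That is 282 × 0.0042 = 1.2 to 282 × 0.0105 = 3.0 subjects.
- p1 = p2 = 5%: 0.02 × 0.95 × 0.05 = 0.00095 and 0.05 × 0.95 × 0.05 = 0.0024, so 5% becomes 5.1% to 5.2%.

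**5. Volume rows.** With volumes v1 and v2 in one period, the period row shows one of them and the total row shows v1 + v2, so the rows need not add up. The volume table keeps the injection closest to schedule and the diary table keeps the earliest diary. For one subject the two tables can therefore describe different injections.

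**The case against.** The strongest defence is that this is a display convention for off-plan cases. The protocol schedules one baseline treatment, one optional touch-up and one optional treatment at month 12, so a second diary within one of these implies an unscheduled injection. Safety analysis is descriptive, all diary data are listed, and the primary endpoint is untouched. The volume rule is stated openly and the total row hides no exposure. Nor can it be said that the affected subjects received the most product, since an extra session might only complete a split treatment. All of this stands, and it keeps the point small. It does not justify calling a figure a maximum when a completed diary has been left out of it.

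A reader might infer something stronger: that every touch-up diary drops out, because SAP 2.5.2 counts touch-up within the initial timepoint. If touch-up rates were 20% to 60% (assumed), that would be 282 × 0.2 = 56 to 282 × 0.6 = 169 diaries, or 0.2/1.2 = 17% to 0.6/1.6 = 37.5% of initial plus touch-up diaries. The documents do not support this as the intended reading. SAP 1.5.3 and 2.5.1 treat touch-up as a separate treatment, and SAP 2.9 ties the diary rule to the exposure rules. Those figures should not be used to grade the point. What survives is that SAP 2.5.3 leaves the term undefined, so a programmer who borrowed the AE timepoints would not be contradicting its text.

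**Conclusion.** The point holds in a limited form. The first-diary rule removes completed diaries from the incidence, maximum-severity and number-of-days summaries, and its effect runs in one direction, towards equal or better apparent tolerability. Protocol 10.5 does not call for it.

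On the more coherent reading it affects only diaries from extra, off-schedule injections. Their number is not in the documents and is probably small. Under an assumed 2% to 5%, about 6 to 14 diaries are omitted and a symptom rate moves by about 1 percentage point or less. Positive correlation between a subject's diaries would shrink this further, as would an extra injection early enough to be partly covered by the first diary.

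The loss of touch-up diaries is a risk of ambiguous wording, not something the SAP prescribes. No conclusion on effectiveness is affected.

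**What to change.** In SAP 2.5.3:
- State that initial treatment, touch-up and re-treatment are separate treatment periods for the diary table.
- Replace the first-diary rule. Where a subject has more than one diary in a period, count a symptom if it is present in any of them and take the worst severity over all of them.
- Report number of days per diary. Simply totalling days would not fit the present table, because two 28-day diaries can give up to 28 + 28 = 56 days while the top category is 14-28. If days are totalled, add a category above 28 and count a calendar day covered by both diaries once.

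In SAP 2.5.1, sum all injections in a period for that period's volume, so that the periods add to the total.

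The cost is SAP wording and minor programming. The diaries and volumes are already collected. Reported symptom rates may be slightly higher.
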